7.8.2 Rescue medication

The use of benzodiazepines as rescue therapy for epilepsy is allowed if taken at a maximum frequency of 1 day per week (with up to 3 doses within 24 hours) during study participation; more frequent use precludes subjects from study participation.

7.9 Blinding

SP0966 is an open-label study; thus, there will be no blinding.

7.10 Randomization and numbering of subjects

Subjects will not be randomized in this study. A unique 5-digit identification number will be assigned by an Interactive Voice/Web Response System (IXRS) to all subjects who sign the ICF at Visit 1. This subject number will be used to identify the subject throughout the study and to maintain subject confidentiality. At subsequent visits, the IXRS will assign the applicable LCM bottle number. Further instructions will be provided in the IXRS manual.

8 STUDY PROCEDURES BY VISIT

All visits occur at the end of the respective week in the study; a window of ± 2 days relative to Visit 2 is applicable for all visits and telephone contacts.

A detailed tabular schedule of study procedures is provided in Section 5.2.

8.1 Baseline Period

8.1.1 Visit 1 (Week -6) Screening Visit

At Visit 1, subjects will be evaluated for their suitability for enrollment. The Screening Visit assessments will be conducted 6 weeks prior to the first administration of LCM. It is acceptable for the Screening assessments to be conducted over >1 day. Prior to the conduct of any study-related procedures, a complete explanation (both verbal and written) of the nature and purpose of the study will be given to the subject (when possible or as required according to local IRBs/IECs) and the subject's parent/legal representative by the investigator (or designee). The subject's parent/legal representative will be requested to sign and date the IRB/IEC-approved ICF. When possible, or as required by the local IRB/IEC, the subject will be requested to give assent to participate in the study.

The subject's eligibility for the study will be determined on the basis of the inclusion/exclusion criteria, signature on an ICF prior to any study-related procedures or evaluations, and the results of the following pretreatment assessments (for further details of the assessments and the required procedures and methods, please refer to Section 9 and Section 11 of this protocol):

- Contact IXRS to obtain unique subject identification number.
- Review seizure history. The subject or caregiver (including parent/legal representative) will be asked how many seizures the subject has had over the past 4 weeks as a historical Baseline.
- Concomitant AED(s) assessment.
- VNS assessment (for subjects with an implanted VNS device).
- Concomitant medication(s) assessment.
- Medical history assessment.
- Complete physical examination.
- Complete neurological examination.

- 12-lead ECG (2 interpretable recordings [20 to 30 minutes apart] to be performed prior to any blood draws and vital signs assessment and, if possible, with the subject in the supine position for approximately 5 minutes preceding the recordings and during the recordings).
- Vital signs (BP and pulse rate, including orthostatic assessments in ambulatory subjects).
- Body weight and height assessment.
- Head circumference in subjects <4 years of age.
- Epilepsy surgery assessment.
- C-SSRS (if applicable). The C-SSRS will be completed for all subjects ≥ 6 years of age.
- Blood sample for clinical chemistry, hematology, and endocrinology.
- Serum pregnancy test (if applicable).
- Urine sample for urinalysis (if applicable). Will be performed for subjects aged 5 to 17 years.
- Tanner Stage (if applicable). The Tanner Stage will be performed only for subjects who are pubescent at Visit 1 or who enter puberty during the course of the study.
- Dispense subject diary and remind subject to complete subject diary on a daily basis.
- AE reporting.

Eligible subjects will be scheduled to return to the clinic (Visit 2, Day 1) approximately 6 weeks ± 2 days after the Screening Visit.

8.1.2 Telephone contact (Week -3)

Three weeks before Visit 2 (± 2 days), the investigator or designee should contact the subject's caregiver (including parent/legal representative) by telephone. The investigator (or designee) should remind the subject's caregiver (including parent/legal representative) to ensure the diary is completed. The following should be performed via telephone:

- Review inclusion/exclusion criteria
- Concomitant medications assessment
- Concomitant AEDs assessment
- Reminder to complete subject diary on a daily basis
- Review withdrawal criteria
- AE reporting

8.2 Titration Period

8.2.1 Visit 2 (Day 1)

Subjects will be asked to return to the clinic on the morning of the day prior to Visit 2 (end of Week 0) to begin 24-hour ambulatory EEG recordings. Scalp electrodes will be attached, and subjects will receive a recording device. Subjects will be asked to return approximately

24 hours later (for Visit 2, Day 1) for removal of the scalp electrodes and return of the recording device. At Visit 2, the investigator should determine whether the subject is still eligible and willing to continue in the study.

The following will be performed prior to the first dose of LCM:

- Review inclusion/exclusion criteria.
- Concomitant AED(s) assessment.
- VNS assessment (for subjects with an implanted VNS device).
- Concomitant medication(s) assessment.
- Complete physical examination.
- Complete neurological examination.
- 12-lead ECG (2 interpretable recordings [20 to 30 minutes apart] to be performed prior to any blood draws and vital signs assessment and, if possible, with the subject in the supine position for approximately 5 minutes preceding the recordings and during the recordings. Recordings should be performed at least 15 minutes after removal of scalp electrodes used for the 24-hour ambulatory EEG recording).
- Vital signs (BP and pulse rate, including orthostatic assessments in ambulatory subjects).
- Body weight and height assessment.
- C-SSRS (if applicable).
- Blood sample for clinical chemistry and hematology.
- Blood sample for LCM and concomitant AED plasma concentrations (before dosing with LCM). Blood sample will be drawn along with clinical chemistry and hematology samples.
- Achenbach CBCL (if applicable); CBCL/1½-5 or CBCL/6-18 for pediatric subjects ≥18 months of age.
- Bayley Scales of Infant and Toddler Development®, Third Edition (Bayley-III Scales) (if applicable). For pediatric subjects <18 months of age at Baseline enrolled in English-speaking countries.
- BRIEF-P (≥2 years to <5 years of age)/BRIEF (≥5 years of age) (version consistent with age at the visit).
- PedsQL for subjects ≥1 month to ≤18 years of age (version consistent with age at the visit).
- Urine sample for urinalysis (if applicable).
- Urine pregnancy test (if applicable).
- Subject diary return/review.
- AE reporting.

- Review withdrawal criteria.
- Contact IXRS.
- Dispense subject diary.
- Reminder to complete subject diary on a daily basis.
- Health care resource use.
- Dispense LCM. Subjects should take the first dose of LCM (based on body weight) in the clinic. The starting dose for subjects taking the oral solution formulation will be 2mg/kg/day, and the starting dose for subjects taking the tablet formulation will be 100mg/day.

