The study will begin with subject screening at Visit 1 and will consist of a 6-week prospective Baseline Period where seizure frequency will be captured through daily seizure diaries. At the end of the Baseline Period, subjects will commence a 6-week Titration Period at Visit 2, where subjects will initiate treatment with LCM (LCM dosing flexibility allowed based on tolerability). Subjects weighing < 50 kg will begin treatment on LCM oral solution 2mg/kg/day, and subjects weighing ≥ 50 kg will begin treatment on LCM tablets 100mg/day (subjects weighing ≥ 50 kg who are unable or unwilling to swallow tablets can be dispensed LCM oral solution instead). The dose will be titrated to a level to optimize tolerability and seizure control, not to exceed 12mg/kg/day (oral solution) for subjects weighing < 50 kg or 600mg/day (tablets/oral solution) for subjects weighing ≥ 50 kg. At the end of the Titration Period (Visit 6), a 12-week Maintenance Period will begin. Subjects must titrate to at least 4mg/kg/day for subjects weighing < 50 kg or 200mg/day (tablets/oral solution) for subjects weighing ≥ 50 kg in order to enter the Maintenance Period. The LCM dose will remain stable throughout the Maintenance Period. Subjects who require a change in dose during the Maintenance Period will be withdrawn from the study. Subjects who require a change in formulation during the Maintenance Period should consult the medical monitor to assess if the subject can continue in the study.

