The study will begin with subject screening at Visit 1 and will consist of a 6-week prospective Baseline Period where seizure frequency will be captured. Subjects/caregivers will maintain a diary to record daily seizure activity from Visit 1 until the end of the study. The subject diary will capture seizure type and seizure frequency information. If all inclusion criteria are met and no exclusion criterion is met, the subject will begin a 6-week Titration Period (LCM dosing flexibility allowed based on tolerability) starting at Visit 2. Subjects will be asked to return to the clinic on the morning of the day prior to Visit 2 to begin 24-hour ambulatory EEG recordings. Subjects will initiate treatment with LCM oral solution at 2mg/kg/day, or LCM tablets at 100mg/day based on body weight. The dose will be titrated to a level to optimize tolerability and seizure control, not to exceed 12mg/kg/day (oral solution) for subjects weighing < 50 kg, or 600mg/day (tablets/oral solution) in subjects weighing ≥ 50 kg. Subjects will increase the LCM dose in a stepwise fashion on a weekly basis to optimize tolerability and seizure control (see Figure 5-1 and Figure 5-2).

Lacosamide doses will be titrated according to the schedules presented in Table 7-1 and Table 7-2.

At the end of the Titration Period (Visit 6), a 12-week Maintenance Period will begin. The LCM dose will remain stable throughout the Maintenance Period. Subjects who require a change in dose during the Maintenance Period will be withdrawn from the study. Subjects who require a change in formulation during the Maintenance Period should consult the medical monitor to assess if the subject can continue in the study.

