5.3 Schematic diagram

Figure 5-1 presents a schematic diagram of the LCM dosing and taper schedule for subjects <50kg receiving the oral solution formulation, and Figure 5-2 presents a schematic diagram of the LCM dosing and taper schedule for subjects ≥ 50 kg receiving the oral solution or tablet formulation.

REDACTED COPY

This document cannot be used to support any marketing authorization application and any extensions or variations thereof.

Figure 5-1: Schematic diagram - LCM dosing and taper schedule for subjects <50kg receiving oral solution formulation

[figure not shown]
[figure not shown]

Figure 5-2: Schematic diagram - LCM dosing and taper schedule for subjects ≥50kg receiving oral solution or tablet formulation

TC=Telephone Contact; V=Visit

Note: LCM dosing is designated as “mg/day”

^a During Titration Period dosage may be adjusted up or down based on investigator’s clinical judgment.

^b Dose reached at the end of Titration Period will be taken throughout Maintenance Period. Subjects may be eligible for participation in the additional open-label study (SP848) if they have completed the Maintenance Period and are taking a minimum dose of 200mg/day (tablets/oral solution). Subjects will begin SP848 on the LCM dose they achieved in the Maintenance Period in SP0966. Subjects who do not complete the full 12 weeks of the Maintenance Period may still be eligible to enter the SP848 open-label study after consultation with the medical monitor.

^c Subjects with doses <150mg/day do not need to taper. See Table 7-5 for exact taper schedule. Taper is not required for subjects participating in the additional open-label study (SP848). A slower or faster taper is permitted if medically necessary. Taper of LCM may not be required for some subjects who discontinue study medication prematurely, depending on the treatment option selected by the investigator in consultation with the subject and/or parent/legal representative. The Taper Period is followed by a Safety Follow-Up Visit 2 weeks (±2 days) after the final dose of LCM and a Safety Follow-Up Telephone Contact 30 days (-1/+3 days) after the final dose of LCM.

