7 STUDY TREATMENT(S)

7.1 Description of IMP(s)

The oral solution formulation contains 10mg/mL of drug substance and is colorless to pale yellow in appearance. Oral solution doses will be measured and administered via a dosing syringe. The tablet formulation will be supplied in doses of 50mg and 100mg. The 50mg tablets are light pink, oval, film-coated tablets debossed with "SP" on one side and "50" on the other. The 100mg tablets are dark yellow, oval, film-coated tablets debossed with "SP" on one side and "100" on the other.

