7.2 Treatment(s) to be administered

Lacosamide will be administered orally bid (at approximately 12-hour intervals in the morning and in the evening). Administration of oral solution by feeding tube is permitted for subjects who are unable to swallow the oral solution. At the end of the Baseline Period and completion of Visit 2, subjects who meet the eligibility criteria will commence a 6-week Titration Period (LCM dosing flexibility allowed based on tolerability).

As described in Section 5.1, subjects will initiate treatment with LCM oral solution at 2mg/kg/day, or LCM tablets at 100mg/day based on body weight. The dose will be titrated to a level to optimize tolerability and seizure control, not to exceed 12mg/kg/day (oral solution) for subjects weighing <50kg, or 600mg/day (tablets/oral solution) in subjects weighing ≥50kg. Subjects will increase the LCM dose in a stepwise fashion on a weekly basis to optimize tolerability and seizure control (see Figure 5-1 and Figure 5-2). During the Titration Period only, back-titration is permitted.

The planned doses for each week of the Titration Period for subjects taking the LCM oral solution and tablet formulations are displayed in Table 7-1.

Table 7-1: Lacosamide dose titration during the Titration Period

Body weight category (formulation)	Flexible doses for the Titration Period by study week					
	Week 1	Week 2	Week 3	Week 4	Week 5	Week 6
<50kg (oral solution)	2mg/kg/day	4mg/kg/day	6mg/kg/day	8mg/kg/day	10mg/kg/day	12mg/kg/day
≥50kg (tablets/oral solution)	100mg/day	200mg/day	300mg/day	400mg/day	500mg/day	600mg/day

LCM=lacosamide

Note: Subjects weighing ≥50kg who are unable or unwilling to swallow tablets can be dispensed LCM oral solution instead.

After completion of Week 1, investigators will assess whether a subject would tolerate a further dose increase or whether a subject should hold the Week 1 dose for a longer duration. This hold will be at the investigator's discretion. The flexible LCM dosing over the remainder of the Titration Period is outlined in Table 7-2.

Table 7–2: Flexible LCM dosing during the Titration Period

Body weight category (formulation)	Target dose increase/week ^a (titration)	Dose decrease per back-titration step		Subsequent dose increase ^b (dose increase after back -titration step)	
		Min	Max	Min	Max
<50kg (oral solution)	2mg/kg/day	1mg/kg/day	2mg/kg/day	1mg/kg/day	2mg/kg/day
≥50kg (tablets/oral solution)	100mg/day	50mg/day	100mg/day	50mg/day	100mg/day

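### Section 8.2.1 sets the starting dose by formulation with no exception for subjects ≥50 kg, so a subject above 50 kg on oral solution would start above the 100 mg/day in Table 7-1.

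*Protocol*

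**What the plan says.** Protocol Section 8.2.1, in the last item of the Visit 2 list, tells the site to dispense lacosamide and give the first dose in the clinic. It states: "The starting dose for subjects taking the oral solution formulation will be 2mg/kg/day". The same sentence gives 100 mg/day for the tablet formulation. The only mention of weight is a parenthesis saying that the first dose is based on body weight. No 50 kg threshold appears, and there is no reference to Table 7-1.

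Table 7-1 in Section 7.2 is organised by weight band. The label of its second row begins "≥50kg (tablets/oral solution", so it covers both formulations, and its Week 1 dose is 100 mg/day. The note below the table says: "Subjects weighing ≥50kg who are unable or unwilling to swallow tablets can be dispensed LCM oral solution instead".

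Other places follow the weight bands. The Summary ties 2 mg/kg/day to subjects below 50 kg and says that "subjects weighing ≥ 50 kg will begin treatment on LCM tablets 100mg/day", with solution available to those who cannot or will not take tablets. Figure 5-2 is titled as the "LCM dosing and taper schedule for subjects ≥50kg receiving oral solution or tablet formulation" and is expressed in mg/day.

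The narrative in Section 7.2 uses the formulation pairing ("subjects will initiate treatment with LCM oral solution at 2mg/kg/day, or LCM tablets at 100mg/day based on body weight"), as do Section 5.1 and SAP Section 2.3. Section 7.2 contains the dosing table itself, and Section 5.1 sends the reader to it: "Lacosamide doses will be titrated according to the schedules presented in Table 7-1 and Table 7-2".

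**The concern.** For a subject above 50 kg on oral solution, the two current instructions cannot both be followed. Section 8.2.1 is written for the visit at which the first dose is dispensed and taken. A site that applies it literally would give a higher first dose than Table 7-1 plans.

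Two things are at stake. One is a first dose in a pediatric study that is higher than intended. The other is whether that dose counts as a deviation. Section 11.1.7 asks for dosing beyond what the protocol prescribes to be recorded. At 70 kg, 140 mg/day complies with Section 8.2.1 but is excessive under Table 7-1, so a site and a monitor could reasonably disagree.

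**Working it through.** **Inputs**

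- Solution starting dose in Section 8.2.1: 2 mg/kg/day, with no weight limit.
- Week 1 dose for subjects at or above 50 kg in Table 7-1: 100 mg/day on either formulation; Week 2: 200 mg/day.
- Solution strength in Section 7.1: "The oral solution formulation contains 10mg/mL of drug substance".
- Dosing is twice daily (Section 7.2). Equal morning and evening doses are assumed here.
- The weights are illustrative assumptions; the documents give no weight distribution.

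**Check of the plan's own figures.** At 50 kg the first row of Table 7-1 gives 2, 4, 6, 8, 10 and 12 mg/kg/day × 50 kg = 100, 200, 300, 400, 500 and 600 mg/day. These equal the six weekly steps of the second row, so the bands meet exactly at 50 kg and the conflict arises only above that weight.

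**Formulas**

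- Daily dose under Section 8.2.1 = 2 × weight.
- Daily excess = 2 × weight − 100.
- Week 1 excess = 7 × daily excess.
- Volume per dose = daily dose ÷ 2 ÷ 10 mg/mL.

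| Weight | Section 8.2.1 | Table 7-1 | Daily excess | Week 1 excess | Volume per dose: Section 8.2.1 vs Table 7-1 |
|---|---|---|---|---|---|
| 50 kg | 100 mg/day | 100 mg/day | 0 | 0 | 5 vs 5 mL |
| 60 kg | 120 mg/day | 100 mg/day | 20 mg (20%) | 140 mg | 6 vs 5 mL |
| 70 kg | 140 mg/day | 100 mg/day | 40 mg (40%) | 280 mg | 7 vs 5 mL |
| 80 kg | 160 mg/day | 100 mg/day | 60 mg (60%) | 420 mg | 8 vs 5 mL |

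**Upper bound on concern.** Section 8.2.1 reaches the planned Week 2 dose when 2 × weight = 200, that is, at 100 kg. Below that weight, the literal first dose is less than the dose planned for one week later.

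**The case against.** The strongest reply is that the dosing section already settles the case. Table 7-1 has a row for exactly these subjects, and Tables 7-2, 7-3 and 7-5, the dose rationale in Section 5.4, the figures and the Summary all use the same bands. Section 5.1 says that formulation follows weight, so naming a formulation can be read as shorthand for a weight band. The parenthesis in Section 8.2.1 supports this reading, because a flat 100 mg/day is based on weight only if a weight band selects it. It is also an inference that sites dose from Section 8.2.1. The interactive response system manual and the pharmacy manual are not among the documents and may be clearer.

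Most of this stands as evidence of intent: the weight-band rule is the one meant. It does not remove the conflict. The parenthesis names no threshold, and 2 mg/kg/day is itself a weight-based dose, so a reader can satisfy both the parenthesis and the formulation rule and still give 140 mg/day at 70 kg. Section 8.2.1 does not send the reader to Table 7-1, and the documents contain no rule on which text prevails. Section 7.10 says only that the response system assigns a bottle number; it describes no dose check.

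The point that the consequence is small also stands. It affects a subgroup of unknown and possibly very small size in a study of about 50. The protocol allows the Week 1 dose to be held and permits back-titration.

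**Conclusion.** The concern holds. Section 8.2.1 is wrong as written for subjects above 50 kg on oral solution: it gives 20%, 40% and 60% more than Table 7-1 at 60, 70 and 80 kg, and the same dose at exactly 50 kg. This is an internal inconsistency in a dosing instruction; the design itself is not in question.

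The practical effect is limited. The literal dose is the same per kilogram as smaller children receive. If the site follows Table 7-1 from Week 2, the excess lasts one week. No primary analysis depends on it. These figures rest on illustrative weights and a literal reading of Section 8.2.1. The number of subjects affected cannot be estimated from the documents. The correction should still be made, because it concerns a child's first dose and takes one sentence.

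**What to change.** In Protocol Section 8.2.1, replace the starting-dose sentence with: <50 kg: 2 mg/kg/day (oral solution); ≥50 kg: 100 mg/day (tablets or oral solution), per Table 7-1.

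Use the same weight-band wording in place of the formulation shorthand in Protocol Sections 5.1 and 7.2 and in SAP Section 2.3.

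The cost is one operative sentence and three matching edits. No new data, procedures or subjects are needed.

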8.2.2 Telephone contacts (Weeks 1 and 3)

At the end of Weeks 1 and 3 (± 2 days), the investigator or designee should contact the subject's caregiver (including parent/legal representative) by telephone. The assessments for these telephone contacts are the same as those performed during the telephone contact at Week -3 in Section 8.1.2 with the exception that inclusion/exclusion criteria do not need to be checked at Weeks 1 and 3.

8.2.3 Visit 3 (Week 2)

At Visit 3 (end of Week 2 ± 2 days), subjects will return for a clinic visit, and the following will be performed:

- Concomitant AED(s) assessment.
- VNS assessment (for subjects with an implanted VNS device).
- Concomitant medication(s) assessment.
- Vital signs (BP and pulse rate, including orthostatic assessments in ambulatory subjects).
- Body weight assessment.
- Urine pregnancy test (if applicable)
- C-SSRS (if applicable).
- 12-lead ECG (2 interpretable recordings [20 to 30 minutes apart] to be performed prior to any blood draws and vital signs assessment and, if possible, with the subject in the supine position for approximately 5 minutes preceding the recordings and during the recordings).
- Subject diary return/review.
- LCM return.
- AE reporting.
- Review withdrawal criteria.
- Contact IXRS.
- Dispense subject diary.

- Reminder to complete subject diary on a daily basis.
- Health care resource use.
- Dispense LCM.

